10.3. Subject Characteristics

Summary for Demographic and Baseline disease characteristics will be presented. These will include age, sex, race, ethnicity, body weight, height, body mass index, duration of asthma, prior use of anti-asthmatic treatments and baseline FEV1 values as well as FEV1 as percent of predicted.

Summary statistics of compliance to study treatment and duration of exposure will be presented.

10.4. Analysis of Efficacy Data

10.4.1. Primary Efficacy Variable

Mean change in Forced Expiratory volume in 1 second (FEV₁) from baseline (visit 3) to Week 4 i.e. end of study visit (visit 5), will be analysed as primary end point.

FEV₁ will be recorded at Visit 5 in the morning, prior to the dosing of inhaled medications.

“Baseline morning FEV₁ readings at visit 3 will be the average of pre dose highest FEV₁ values at two time points (i.e., Patient needs to perform one baseline Spirometry session with minimum of 3 acceptable readings and then after a gap of minimum 30 minutes, one more baseline session will be performed with minimum of 3 acceptable readings. Highest value from both the sessions will be noted. Average of both the highest readings will be considered as baseline FEV₁ value). Sampling need to be taken on the same time (with a window period of \pm 30 min) of day as used for first day of a 4 week treatment on the last day of a 4-week treatment.

10.4.2. Primary Analysis

The primary endpoint is the change from baseline to week 4 for FEV₁. The statistical evaluations for this endpoint are described below.

Equivalence

Compound Hypothesis to be tested is

$H_0: \mu_T / \mu_R \leq \theta_1 \quad \text{or} \quad \mu_T / \mu_R \geq \theta_2$ versus $H_A: \theta_1 < \mu_T / \mu_R < \theta_2$

Where μ_T = mean of test treatment, and μ_R = mean of reference treatment

Analysis of covariance (ANCOVA) will be used to evaluate the mean change in FEV1 at week 4, for the test and reference treatments using baseline FEV1 as a covariate and treatment and clinical site as factors. The 90% confidence interval will be computed by Fieller's Theorem based on the results from the ANCOVA. The 90 % confidence interval on the test-to-reference ratio must contain within the interval 80.00% to 125.00% for the test and reference products to be considered equivalent to each other.

Superiority

Analysis of Covariance will be used to compare each active treatment with placebo using Baseline FEV1 as covariate and clinical site and treatment as factor. If the active treatment shows a greater increase in FEV1 from baseline than that for the placebo, and the difference between it and the placebo is statistically significant ($p < 0.05$), then the active treatment will be considered superior to placebo. Superiority must be shown for both active treatments over placebo for the equivalence evaluation between the test and reference treatments to be considered valid.

10.4.3. Secondary Efficacy Variables

- Mean change in FeNO value from base line (visit 3) to end of study visit (visit 5)
- Percentage of subjects with reduction of FeNO from Baseline (Visit 3) to End of Study (Visit 5)

10.4.4. Secondary Analysis

Descriptive Summary statistics will be presented for all secondary endpoints for active treatment groups.

Number and percentage of subjects meeting the criteria for reduction (atleast 20 % for FeNO \geq 50 ppb values and atleast 10 % for FeNO $<$ 50 ppb) in FeNO will be presented.

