	
Note: “Baseline morning FEV1 readings at visit 3 will be the average of pre dose highest FEV1 values at two time points (i.e., Patient needs to perform one baseline Spirometry session with minimum of 3 acceptable readings and then after a gap of minimum 30 minutes, one more baseline session will be performed with minimum of 3 acceptable readings. Highest value from both the sessions will be noted. Average of both the highest readings will be considered as baseline FEV1 value). Sampling need to be taken on the same time (with a window period of ± 30 min) of day as used for first day of a 4 week treatment on the last day of a 4-week treatment.
 
Secondary Endpoints
 
 • Mean change in FeNO value from base line (visit 1 & 3) to end of study visit (visit 5) • Percentage of subjects with reduction of FeNO from Baseline (Visit 1 & 3) to End of Study (Visit 5) 	
Safety Endpoints	Safety will be assessed on the basis of reported adverse events, serious adverse events and laboratory assessments.	
Statistical Analysis	
 1. Primary endpoint will be analyzed by comparing between Test and Reference groups for Equivalence and further comparing between Test group versus Placebo and Reference group versus Placebo for Superiority. 2. Test group will be declared equivalent to Reference group, if the 90 % CI of the ratio between the Test product and Reference product for the primary endpoint is within the limits of 80.00% - 125.00% at the end of study (Day 42 \pm 2). 3. At study conclusion, Test and Reference groups will each be evaluated for Superiority over Placebo ($p < 0.05$) at Visit 5/ EOS (Day 42 \pm 2). For this the mITT analysis population and Last Observation Carried Forward (LOCF) will be used. 	

Table – I: TABLE OF EVENTS

Procedure	Screening Period		Run-in Period	Treatment Period		End of Study
	-7 days	Day 0	Day 1 to Day 14	Day 15 + 1	Day 21±1	Day 42±2
Visit	1	2	--	3	4	5
Informed consent	X	--	--	--	--	--
Eligibility criteria	X	--	--	X	--	--
Demography	X	--	--	--	--	--
Medical and Medication History ¹	X	--	--	--	--	--
General & Systemic Examination ²	X	X	--	X	X	X
Vital signs ³	X	X	--	X	X	X
Serum Pregnancy Test (for females of child bearing potential)	X	--	--	--	--	--
Urine Pregnancy Test (for females of child bearing potential)	--	--	--	X	--	X
Clinical Laboratory Test ⁴	X	--	--	--	--	X
12 lead ECG	X	--	--	--	--	--
Chest X-Ray (PA view)	X	--	--	--	--	--
FeNO Estimation	X	--	--	X	--	X

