4.3. Placebo Run in period (Day 1 to Day 14)

During the Run-in period, subjects will administer one inhalation of placebo twice daily for 2 weeks duration. Subjects will be requested to mention any concomitant medications used during this time in their subject diaries. During this period, pre-study corticosteroids/ long-acting bronchodilators will be washed out and FEV1 baseline values will be established.

Table IV Procedures from Day 1 to Day 14

Procedure	Run-in Period
	Day 1 to Day 14
Placebo administration	One inhalation two times daily from Day 1 to Day 14
Concomitant medication check	X
Adverse event recording	X

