6.0 STUDY ENDPOINTS

6.1. Efficacy Endpoints

Primary Endpoint:

- Mean change in Forced Expiratory volume in 1 second (FEV₁) from baseline (visit 3) to end of study visit (visit 5).

Note: “Baseline morning FEV₁ readings at visit 3 will be the average of pre dose highest FEV₁ values at two time points (i.e., Patient needs to perform one baseline Spirometry session with minimum of 3 acceptable readings and then after a gap of minimum 30 minutes, one more baseline session will be performed with minimum of 3 acceptable readings. Highest value from both the sessions will be noted. Average of both the highest readings will be considered as baseline FEV₁ value). Sampling need to be taken on the same time (with a window period of \pm 30 min) of day as used for first day of a 4 week treatment on the last day of a 4-week treatment.

Secondary Endpoints:

- Mean change in FeNO value from base line (visit 1 & 3) to end of study visit (visit 5)
- Percentage of subjects with reduction of FeNO from Baseline (Visit 1 & 3) to End of Study (Visit 5)

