7.0 ASSESSMENT OF STUDY ENDPOINTS

7.1. Assessment of Efficacy Endpoints

The primary efficacy endpoint will be evaluated on mean change in Forced Expiratory Volume in 1 second (FEV1) from baseline (Visit 3) to end of study (Visit 5).

The secondary efficacy endpoints will be evaluated on mean change in FeNO value from baseline (visit 1 & 3) to end of study visit (visit 5) and percentage of subjects with reduction of FeNO from baseline (visit 1 & 3) to end of study visit (visit 5).

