10.5. Safety Analysis

Summary of adverse events, Treatment Emergent Adverse Events, Serious adverse event, events leading to discontinuation and treatment related adverse events will be presented for each arm.

Summary of Vital signs and Laboratory parameter values at relevant time-points as well as change from baseline will be presented. Summary of use of various concomitant medications will be presented. By Subject data listings will be presented for all safety data captured on CRF/eCRF.

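### Protocol 10.4.4 limits the FeNO summaries to the active arms, and the FeNO baseline is defined in two ways (low impact: both endpoints are descriptive)

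*Protocol*

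**What the plan says.** **Arms summarised.** Section 10.4.4 reads: "Descriptive Summary statistics will be presented for all secondary endpoints for active treatment groups". The sentence after it, beginning "Number and percentage of subjects meeting the criteria for reduction", gives the responder rule and names no arm. The rule is a fall of at least 20% where FeNO is 50 ppb or more, and at least 10% below that. The safety section is explicit about all arms: "treatment related adverse events will be presented for each arm" (Section 10.5). FeNO itself is collected without regard to arm. Table I schedules it at Visits 1, 3 and 5, and Sections 4.4 and 4.6 make no exception for placebo.

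**Baseline.** The endpoints are defined in four places:

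- Synopsis: "Mean change in FeNO value from base line (visit 1 & 3) to end of study visit (visit 5"), with the responder endpoint worded in the same way.
- Section 6.1: "Percentage of subjects with reduction of FeNO from Baseline (Visit 1 & 3) to End of Study (Visit 5"), with the mean change worded in the same way.
- Section 7.1: "mean change in FeNO value from baseline (visit 1 & 3) to end of study visit (visit 5"), and likewise for the percentage.
- Section 10.4.3: "Mean change in FeNO value from base line (visit 3) to end of study visit (visit 5"), and Visit 3 alone for the percentage too.

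The protocol does not say whether Visits 1 and 3 are to be averaged or reported as two separate changes.

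**The concern.** These are two separate faults in the same small set of endpoints.

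First, the mean-change summary is active-only on its natural reading, and the responder summary is ambiguous. A fall of 10% or 20% between two single FeNO readings can arise from ordinary within-subject variation. Results from the active arms alone therefore cannot show that either product lowered FeNO. The placebo arm would supply that reference, its data are already being collected, and the text leaves them out.

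Second, one endpoint has two definitions. A subject can be a responder on one baseline and not on the other. An analysis plan written to follow the protocol cannot agree with all four passages. If the choice stays open, it could be made after results are known.

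Neither fault touches the primary analysis. Randomisation also means that no between-arm bias is expected under either baseline.

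**Working it through.** **1. The plan's own figures, to confirm that nothing primary moves.** Section 10.1 gives changes of 0.24, 0.24 and 0.05 L and a CV of 115.5% of the Reference mean, so SD = 1.155 × 0.24 = 0.2772 L.

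- Equivalence: 470 PP subjects per active arm, Fieller 90% CI within 0.80–1.25, 400,000 simulated trials. Power is 0.802 (stated 0.80).
- Superiority: difference 0.24 − 0.05 = 0.19 L, 588 against 294. Power is above 0.999 (stated >0.99).
- Enrolment: 1470/0.95 = 1548 after rounding up (stated 1550).

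All three reproduce, and none involves FeNO.

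**2. Responder rate without any drug effect.** The protocol gives no FeNO mean or variance, so every input below is assumed.

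- ln(FeNO) at a visit = subject level + visit error.
- Subject level: median 30 or 40 ppb, SD 0.5 on the log scale.
- Visit error SD: s = √ln(1 + CV²), with within-subject CV 10–25%.
- Entry: FeNO above 25 ppb at Visits 1 and 3 (Section 5.2, criterion 5).
- The 50 ppb tier is read at the baseline value.
- 3,000,000 subjects simulated per setting before the entry filter.

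A hand check shows the mechanism. Ignoring entry selection, P(fall ≥ 10%) = Φ(ln 0.9 / (s√2)) and P(fall ≥ 20%) = Φ(ln 0.8 / (s√2)). At CV 15%, s = 0.149 and s√2 = 0.211. The probabilities are Φ(−0.50) = 30.9% in the lower tier and Φ(−1.06) = 14.5% in the upper tier. The simulated rate should fall between them, and does (23.8% and 27.4%).

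Each cell shows median 40 / median 30 ppb, Visit 3 baseline:

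| CV | No drift | FeNO drifts up 10% |
|---|---|---|
| 10% | 15.1 / 18.4% | 4.5 / 5.8% |
| 15% | 23.8 / 27.4% | 12.0 / 14.3% |
| 20% | 29.8 / 33.4% | 18.8 / 21.6% |
| 25% | 34.1 / 37.7% | 24.3 / 27.3% |

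**3. Precision of a placebo column.** The 95% half-width is 1.96 × √(p(1−p)/n). With the planned 294 placebo mITT subjects it is 2.5 points at p = 0.05, 4.1 at 0.15, 5.1 at 0.27 and 5.5 at 0.38. With 235 (PP) it is 2.8, 4.6, 5.7 and 6.2. A placebo rate would therefore be estimated well enough to be useful.

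**4. Effect of the baseline visit.** Same model, comparing Visit 1 with Visit 3 as baseline:

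| CV | Status differs, no drift | Status differs, drift |
|---|---|---|
| 10% | 16.1 / 18.7% | 6.2 / 7.8% |
| 15% | 22.0 / 23.6% | 13.8 / 15.6% |
| 20% | 24.8 / 25.5% | 19.0 / 20.2% |
| 25% | 26.2 / 26.2% | 22.1 / 22.7% |

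The group percentage is the same on either visit to within 0.1 point when prior treatment has no effect on Visit 1. If the baseline is instead read as the mean of the two visits, the rate moves by −2.0 to +0.5 points without drift and stays within 2 points with it.

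If prior inhaled corticosteroid had lowered Visit 1 FeNO in half of subjects, the Visit 1 rate falls below the Visit 3 rate by:

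- a 10% reduction: 3.9–5.4 points without drift, 1.6–3.5 with drift;
- a 20% reduction: 5.8–8.0 points without drift, 1.7–5.7 with drift.

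**5. Is such a Visit 1 effect plausible?** The protocol gives mixed signals. Section 4.3 says of the run-in: "During this period, pre-study corticosteroids/ long-acting bronchodilators will be washed out". Section 4.2 says the same, and Section 5.2 (criteria 6, 9 and 10) describes subjects stable on existing treatment who can stop it during run-in. Section 9.7, however, prohibits corticosteroids from four weeks before enrolment. These passages must be reconciled; no rule is proposed here.

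**The case against.** The strongest reply concerns the first fault. Section 10 calls itself a general description and leaves the list of displays to the statistical analysis plan, and the columns of a descriptive table are a display choice. Section 10.4.4 does not say that placebo is excluded. No objective asks whether either product lowers FeNO: efficacy is judged on FEV1, and the secondary objective is safety and tolerability. A Test-beside-Reference display also suits an equivalence trial. Much of this stands. The analysis plan could widen the display, and omitting placebo invalidates no planned conclusion. What remains is that the protocol does not leave the arms open: it names the active groups. The sentence is better corrected than overridden.

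On the second fault, naming both visits could mean two changes, Visit 1 to 5 and Visit 3 to 5, of which Section 10.4.3 lists one. That reading is possible. Even so, the four passages do not list the same endpoints, and nothing says which reading is intended.

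The magnitudes rest wholly on assumed FeNO inputs, so the ranges are illustrative. The half-widths further assume a Visit 5 FeNO value for every counted placebo subject. Table I has no on-treatment FeNO before Visit 5, and Section 10.4.5 specifies imputation only for FEV1. Both limits are accepted. The two faults themselves rest on the text, not on the simulation.

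**Conclusion.** Both faults hold, and both are low in impact. The FeNO summaries are stated for the active groups although placebo FeNO is collected, and the FeNO baseline differs between Section 10.4.3 and the three other places that define it.

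Under the assumed variability, chance alone yields a responder rate between 5% and 38%, so an active-only percentage cannot be read as a drug effect. The choice of baseline visit reclassifies 6–26% of individual subjects. It moves the group percentage by 2–8 points only if prior inhaled corticosteroid had lowered Visit 1 FeNO by the assumed 10–20% in half of subjects.

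The equivalence and superiority decisions, the error rate and the sample size do not change. The correction should be made because it is nearly free and settles the definition before unblinding.

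**What to change.** - **Section 10.4.4:** state that FeNO mean change and the percentage with reduction are presented for Test, Reference and Placebo, and name the three arms in the responder sentence.
- **Synopsis, Sections 6.1 and 7.1:** use Visit 3 as the FeNO baseline, to agree with Section 10.4.3. Visit 3 is the pre-dose assessment on the day of randomisation and is also the FEV1 baseline visit. Show Visit 1 FeNO descriptively.
- **Alternative:** if the sponsor wants both changes, define and label each one separately in all four places.
- **Sections 4.2, 4.3, 5.2 and 9.7:** reconcile what they say about corticosteroid use before and during run-in, so that the meaning of a Visit 1 FeNO value is clear.

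The FeNO changes cost one more table column, three baseline wording changes and the edit to 10.4.4. They need no new data, visits or tests.

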10.4.5. Imputation for Missing Data

For subjects included in the mITT population, and for those PP subjects who discontinue due to lack of treatment efficacy, Last Observation Carried Forward (LOCF) imputation will be used to impute missing EOS values for FEV1. If a subject discontinued due to lack of efficacy does

not have a post baseline value, then the baseline value will be carried forward. No imputation will be performed for missing safety data.

10.5. Safety Analysis

Summary of adverse events, Treatment Emergent Adverse Events, Serious adverse event, events leading to discontinuation and treatment related adverse events will be presented for each arm.

Summary of Vital signs and Laboratory parameter values at relevant time-points as well as change from baseline will be presented. Summary of use of various concomitant medications will be presented. By Subject data listings will be presented for all safety data captured on CRF/eCRF.

11.0 QUALITY CONTROL AND QUALITY ASSURANCE

According to the International Conference on Harmonization (ICH) Harmonized Tripartite Guideline for Good Clinical Practice (ICH-GCP), AXIS/sponsor is responsible for implementing and maintaining quality assurance and quality control systems with written SOPs.

Quality control will be applied to each stage of data handling.

The following steps will be taken to ensure the accuracy, consistency, completeness, and reliability of the data:

- Site Initiation visit
- Early site visits post-enrollment
- Routine site monitoring
- Ongoing site communication and training
- Data management quality control checks
- Continuous data acquisition and cleaning
- Internal review of data
- Quality control check of the final clinical study report

In addition, sponsor and/or AXIS Clinical Quality Assurance (CQA) Department may conduct periodic audits of the study processes, including, but not limited to study site, site visits, central laboratories, vendors, clinical database, and final clinical study report. When audits are conducted, access must be authorized for all study related documents including medical history and concomitant medication documentation to authorized sponsor's representatives and regulatory authorities.

11.1. Direct Access to Source Documents and Study Monitoring

Investigator will prepare and maintain adequate and accurate source documents to record all observations and other pertinent data for each subject entered into the study.

Investigator will allow the sponsor, AXIS, and authorized regulatory authorities to have direct access to all documents pertaining to the study.

The Sponsor has engaged the services of a Contract Research Organization (CRO), AXIS Clinicals, to perform all monitoring functions within this clinical study. AXIS' monitors will work in accordance with sponsor or AXIS' SOPs and have the same rights and responsibilities as monitors from the sponsor organization. Monitors will establish and maintain regular contact between the PI and the sponsor.

Monitors will evaluate the competence of the study site, informing the sponsor about any problems relating to facilities, technical equipment or medical staff. During the study, monitors

will check that written informed consent has been obtained from all subjects correctly and that data are recorded correctly and completely. Monitors are also entitled to compare entries in CRF/eCRF with corresponding source data and to inform the PI of any errors or additions. Monitors will also direct adherence to the protocol at the investigator site. They will liaise with the sponsor for supply of study drugs and ensure appropriate storage conditions are maintained at investigator site.

Monitoring visits will be conducted according to the, ICH E6 Guideline for GCP, Monitoring plan and applicable local regulations. The monitor will visit the site while subjects are enrolled in the study at regular intervals according to the monitoring plan. The monitor will make written reports to the Sponsor on each occasion when contact with the PI is made, regardless of whether it is by phone or in person.

During monitoring visits, entries in the CRFs/ eCRFs will be compared with the original source documents (source data verification).

During the monitoring visit, the following items must be accessible for review but not limited to:

- Source documents, including ICFs, for all screened subjects (Monitor will conduct 100% source document verification)
- CRFs/ eCRFs for all subjects
- Investigational Product Accountability
- Site Master File
- Drug supply and clinical supply cabinets
- Storage of lab samples and study medication

All study staff will also need to make themselves available for review of monitoring issues.

11.2. Data Management/ Coding

Data generated within this clinical study will be handled according to relevant SOPs of the Clinical Data Management department of AXIS. In addition, inconsistency in data identified during the data cleaning process is resolved by issuing queries to site. The AE terms reported in the study will be coded using MedDRA.

11.3. Quality Assurance Audit

Investigator sites, the study database and study documentation may be subject to Quality Assurance audit during the course of the study by the Sponsor or AXIS. In addition, inspections may be conducted by regulatory bodies at their discretion.

The PI must notify Sponsor or AXIS promptly of any inspections scheduled by regulatory authorities.

11.4. Data Collection

Entries in CRF/eCRFs legible entries will be made. Any correction to the entered data will be made as per the CRF/ eCRF filling instructions. All corrections shall be authenticated with proper audit trail. Accuracy of the data will be attested by signatures off investigator. For laboratory values, Laboratory reports will be considered as source document.

For laboratory values, laboratory reports will be considered as source document.

12.0 ETHICS

12.1. Ethics Committee

Ethics committee (EC) approval will be obtained from an EC registered with CDSCO. PI will provide the Sponsor or AXIS with documentation of Institutional Ethics Committee (IEC) approval of the protocol, ICF and all documents required as per applicable regulations before the study may begin at the study sites. EC shall maintain all the study records for not less than 5 years from the date of study completion or termination of the trial. PI will supply documentation to the Sponsor or AXIS of required EC's annual renewal of the protocol, and any approvals of revisions to the informed consent document or amendments to the protocol.

The PI will report promptly to the EC, any new information that may adversely affect the safety of subjects or the conduct of the study. Similarly, the PI will submit written summaries of the study status to the EC annually, or more frequently if requested by the EC. Upon completion of the study, the PI will provide the EC with a brief report of the outcome of the study, if required.

